Also unanswered is the degree to which survivors known to have hypertension, dyslipidemia, or diabetes are adequately treated (undertreatment). We are unaware of studies that have attempted to examine CV risk factor undertreatment among childhood cancer survivors, and such studies are rare among survivors of adult cancers.²⁷⁻³¹ Our prior research showed that survivors with these CV risk factors, defined on the basis of medication use, were at significantly greater risk of more serious CV events (e.g., ischemic heart disease, heart failure) vs. other survivors.^{7,17} Thus, we hypothesize that survivors may be significantly undertreated even when diagnosed. The drivers of undertreatment may be related to healthcare providers not intervening sufficiently and/or non-adherence to appropriate interventions among survivors themselves.^{27,32,33}

TABLE 2. Prevalence of selected CV risk factors by 10-year age groups, stratified by CV-risk status* among the original CCSS cohort (n=13,060) and a sibling comparison group (n=4,023).

The study's intervention will feature an IOM-recommended survivorship care plan [SCP], which is designed to promote knowledge/awareness of personal health risks among survivors and to help disseminate that information to primary healthcare providers.³⁴ Prior research has shown that >80% of adult survivors of childhood cancer are followed by primary care providers,^{25,26,35} and that while the majority of internists and family practitioners report caring for childhood cancer survivors, receipt of a SCP remains uncommon and the vast majority of surveyed providers do not report familiarity with long-

[figure not shown]
term follow-up guidelines for childhood cancer survivors.^{22,23} Our SCP intervention also will be enhanced by the use of recently developed and validated individual CV risk predictors our group has created specifically for childhood cancer survivors (Tables 1, 2). Although the SCP is by itself a tool to foster self-management, we will further supplement it with well-established, focused chronic disease self-management strategies now being applied to improve coordination of cancer survivorship care (Figure 2).³⁶⁻³⁹ Collection of directly measured data also offers an opportunity to further refine risk prediction in the future, beyond using self-report alone (Table 2).

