PROJECT VISION (PI: [name]; Livestrong; 2003-05) enrolled 62 (86% participation rate) adult-aged Hodgkin lymphoma survivors at increased risk for either breast cancer or cardiomyopathy to test the acceptability of an IOM-based SCP supplemented by a study website and an effort to engage participants' primary care providers.⁴³ 92% of participants completed a 6-month post-intervention survey; 75% remembered receiving, reading, and understanding the SCP. Among participants, prior knowledge of mammogram and echocardiogram screening recommendations was low (32% and 12% respectively). During the 6-month study period, 41% and 20% of eligible respondents obtained a mammogram and echocardiogram, respectively, with another 35% (for both tests) planning to do so

FIGURE 3. Yield of directly measured data in relation to self-report among randomly selected CCSS participants (n=175).

*Per self-report. †Among those with self-reported condition if home sampled value was beyond standard therapeutic range. ‡No prior self-reported history of respective condition with abnormal value.

within the next 6 months. As such, these data guide our planned intervention follow-up period of 12 months between assessments. Similar to other studies,⁴⁴ website usage was limited among these young adult survivors (29% visit rate). Primary care providers demonstrated limited engagement: only 19% of providers volunteered to participate; none visited the study website or contacted the study team.⁴³

The ECHOS trial (co-PI: [name]; R01 CA136912; 2009-13) extended the methods in VISION to directly test the efficacy of a SCP supplemented by 2 nurse practitioner-led phone self-management counseling sessions on cardiomyopathy screening (vs. mailed SCP alone).⁴⁵ After 1-year, the randomized intervention group had higher rates of obtaining recommended echocardiograms per self-report validated by medical records (52% vs. 22% SCP alone [$p<0.001$]; RR 2.3, 95% CI 1.7-3.1). The intervention group also was less likely to report lack of physician recommendation as a reason for not obtaining an echocardiogram, suggesting that the counseling further enhanced communication between recipients and their primary care provider beyond what a SCP alone would have accomplished.⁴⁶ The study had an 87% retention rate at 1-year follow-up (n=411 of 472).⁴⁵

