13.0 STATISTICAL CONSIDERATIONS

13.1 Aim 1 Analytic Plan

Hypothesis: Approximately 60% of participants will have an abnormal CV risk-factor finding that meets clinical intervention thresholds, and among those with abnormalities, 40% will be undertreated and 80% newly diagnosed.

Primary analyses: We will calculate the prevalence of hypertension, dyslipidemia, and diabetes by self-report and by physiologic measurement. We will then calculate the proportions (with exact 95% confidence intervals) of participants who may be underdiagnosed as well as the proportions undertreated (like **Figure 3**). We will calculate the prevalence of directly measured pre-diabetes separately. **Secondary analyses:** We will examine whether rates differ by: sex; current age; time since cancer diagnosis; obese ($BMI \geq 30 \text{ kg/m}^2$) vs. not; health insurance vs. not; recent history of being seen in a dedicated long-term follow-up clinic for survivors vs. not; and lifestyle factors (smoking, low fruit/vegetable intake, low physical activity).

Sample size considerations: Based on prevalence estimates from CCSS surveys and our pilot (**Table 2, Figure 3**), we expect ~60% of high CV risk participants ($n \sim 480$) to have an abnormal CV risk factor measurement; prevalence of individual risk factors ranging 20-40% (less when stratified by underdiagnosis/undertreatment status). With an overall sample $n=800$, we expect reasonable precision for our primary prevalence estimates (**Table 9**). Power to detect differences <10% in secondary analyses may be more limited.

TABLE 9. Estimated power for Aim 1 analyses.		
Prevalence \pm 95% CI	Minimum detectable proportions*	
N=800	N=320:480	N=200:200
5% \pm 1.5%	5% vs. 1/11%	5% vs. 0/14%
20% \pm 2.8%	20% vs. 12/29%	20% vs. 10/33%
50% \pm 3.5%	50% vs. 40/60%	50% vs. 36/64%

*2-sample Fisher's exact test, 80% power, $\alpha=0.05$.

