Secondary analyses: In case survivors who were newly diagnosed (i.e., underdiagnosed) following their 1st home visit differ in their response to the intervention vs. those previously diagnosed but undertreated, we will examine estimates stratified by diagnosis status at the 1st home visit. For similar reasons, we also will examine estimates if pre-diabetes are excluded. In our primary model, we also will explore whether differences vary by sex, current age, time since cancer diagnosis, obese (BMI ≥ 30 kg/m²) vs. not, health insurance vs. not, and recent history of being seen in a dedicated long-term follow-up clinic for survivors vs. not. We also will explore, among intervention participants, whether action plan scores from the 4-month session are associated with differential undertreatment rates (as a single parameter). Finally, we plan to also compare across the study arms, the measured CV risk factor values from the 2nd home visit separately: 1) average systolic pressure, 2) average diastolic pressure, 3) LDL, 4) triglyceride, 5) blood glucose, and 6) HbA1c. For this subanalysis we will use linear models, adjusting for the value at the 1st home visit as a covariate.

Sample size considerations: Assuming 60% of Aim 1 participants (n=800) meet Aim 2 eligibility with a subsequent conservative 20% drop-out rate, ~380 survivors (190/arm) would have complete data. The study would be 80% powered ($\alpha=0.05$) to detect RRs ≤ 0.88 (i.e., $\geq 12\%$ reduction in the intervention vs. control group) if the prevalence of having an undertreated CV risk factor among controls after the 2nd home visit was 90% (10% reduction from baseline). If controls had an unlikely 50% reduction, we can still detect RRs ≤ 0.71 . Analyses stratified by initial underdiagnosis or undertreatment status (~75-150/arm) will be able to detect RRs ≤ 0.79 to ≤ 0.86 , respectively. Systematic reviews have reported RRs 0.6-0.8 for strategies similar our proposed interventions in the general population.^{64,65} For continuous outcomes (secondary analyses), we will be powered to detect change equaling $\sim 30\%$ of 1 standard deviation, which equates to 5 mmHg systolic blood pressure, 3 mmHg diastolic pressure, 10 mg/dL LDL, 30 mg/dL triglyceride, 10 mg/dL glucose, and 0.3% HbA1c. Differences within these ranges have been reported by others for interventions conducted in the general population.⁶⁶⁻⁶⁸

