Post-intervention analysis: Among Aim 2 participants (and their designated healthcare provider), we will examine the differences between intervention and control groups following the 2nd home visit with respect to 1) survivor knowledge [chi-square test], 2) survivor self-efficacy [t-test or Wilcoxon rank-sum], 3) survivor-reported medication adherence [t-test or Wilcoxon rank-sum], and 4) provider-reported knowledge and self-efficacy [chi-square tests] related to the care of childhood cancer survivors. All analyses will be intent-to-treat and include all survivors and providers with available end points. Subanalyses can stratify these outcomes by initial underdiagnosis vs. undertreatment status. *We also will analyze practice changes over the 1-year intervention period using clinical records.* This includes comparing [chi-square test] whether documentation rates differ across study arms of: 1) any CV-related screening, 2) CV-related interventions [both lifestyle and drug prescriptions], and 3) treatment intensity (**Table 7** earlier). If any survivors share the same healthcare provider, we will apply bootstrap methods to account for the effects of clustering. In secondary analyses, we will determine, via logistic regression adjusting for randomization status, whether providers of survivors who remain undertreated have lower self-reported knowledge and self-efficacy related to the care of childhood cancer survivors vs. providers of survivors no longer undertreated.

Sample size: For covariates assessed at baseline in Aim 3, we will be able to detect differences $\geq 5\%$, RRs $\leq 0.8 / \geq 1.2$, and $\geq 20\%$ of 1 standard deviation (**Table 10**). Among randomized participants (240/arm) and subanalyses (e.g., analyzing undertreatment, underdiagnosis separately: $\sim 75-150$ /arm), detectable differences will be less.

Covariate frequency	Baseline* N=320:480	Post-intervention & subanalyses		
		240:240	150:150	75:75
10% (e.g., primary care provider self-efficacy towards childhood cancer survivorship care ^{27,28})	5%/17% RR 0.5/1.7	3%/20% RR 0.3/2.0	2%/22% RR 0.2/2.2	- /28% RR -/2.8
25% (e.g., MHLC self-controlling or worried typologies ⁶⁹ ; survivor anthracycline self-knowledge ⁷⁰)	17%/34% RR 0.7/1.4	15%/37% RR 0.6/1.5	12%/40% RR 0.5/1.6	8%/47% RR 0.3/1.9

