60% (e.g., MHLC collaborating typology ⁶⁹ ; survivor radiotherapy self-knowledge ⁷⁰ ; high medication adherence ^{30,31,67,71,72})	50%/70% RR 0.8/1.2	47%/72% RR 0.8/1.2	44%/75% RR 0.7/1.3	37%/81% RR 0.6/1.3
% standard deviation (e.g., MMAS-4, ⁶⁰ survivor self-efficacy ⁵⁶)	20%	26%	33%	46%

Potential pitfalls / solutions: Self-reported medication adherence is not as accurate as data from pharmacy databases.¹⁰⁰ However, use of these databases is unlikely to be feasible even in large integrated health systems given the relative rarity of childhood cancer survivors. Given upfront randomization, any reporting biases should be similar across study arms. Should our study uncover a suggestive association with adherence, this would provide data to support the use of more expensive medication monitoring devices in a follow-up study.¹⁰⁰ We also anticipate some missing healthcare provider responses. It is possible that providers on the intervention arm who receive the SCP could be more motivated to respond (all providers will get clinically relevant results from home visits). We will closely monitor response rates for providers across the study arms, and will compare the characteristics of responding vs. non-responding providers using American Medical Association databases (physicians only) and publically available information from state licensing boards and the internet (physicians and other providers).^{28,102} In sensitivity analyses, we can examine the differences across study arms after adjustment for characteristics that appear to differ between responding and non-responding primary healthcare providers.

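### Table 10 sizes the provider self-efficacy comparison at 240 per arm, which needs a responding provider for every randomized survivor; the plan's own 20% drop-out leaves 75-79% power for 10% versus 20%, and any provider non-response lowers it further

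*Combined protocol and SAP*

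**What the plan says.** Section 13.3 compares the arms after the 2nd home visit on "provider-reported knowledge and self-efficacy [chi-square tests] related to the care of childhood cancer survivors" and includes providers with available end points. The sample size paragraph introduces the post-intervention numbers with "Among randomized participants (240/arm) and subanalyses"; the subanalyses, at about 75 to 150 per arm, are illustrated by analysing underdiagnosis and undertreatment separately. In Table 10 the row labelled "10% (e.g., primary care provider self-efficacy towards childhood cancer survivorship care" prints 3%/20% at 240:240, 2%/22% at 150:150, and no lower value with 28% as the upper value at 75:75.

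The pitfalls paragraph of 13.3 says "We also anticipate some missing healthcare provider responses". It plans to monitor response by arm, compare responding with non-responding providers, and adjust in sensitivity analyses. It gives no expected response rate.

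Section 7.5 places the provider survey after the 2nd home visit. Section 13.2 assumes 20% drop-out, leaving about 190 survivors per arm. The one provider participation figure is in section 2.2, on an earlier care-plan study: "Primary care providers demonstrated limited engagement: only 19% of providers volunteered to participate".

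**The concern.** The 240 counts randomized survivors, but the unit in this comparison is a returned provider survey. A survey comes back only if the survivor reaches the 2nd home visit, has a designated provider, and that provider replies. The printed detectable difference allows for none of these steps. On the second, section 2.1 says "Prior research has shown that >80% of adult survivors of childhood cancer are followed by primary care providers", and section 7.5 makes arrangements for participants who have no current provider.

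The synopsis lists the between-arm difference in provider knowledge and self-efficacy as a secondary endpoint, and it is the provider half of the second Aim 3 hypothesis. A reader who sets a null result against the 240:240 cell would think that a doubling from 10% to 20% had probably been excluded. With far fewer responding providers, it would not have been.

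**Working it through.** **Inputs.** Reference proportion 10%, detectable proportions 3% and 20%, and 240 per arm come from Table 10. Chi-square is the test named for this outcome in 13.3. The readable text gives no test or power for Table 10, so I take them from the Table 9 footnote ("2-sample Fisher's exact test, 80% power", alpha 0.05), treat alpha as two-sided, and show both tests. The 20% drop-out and 190 per arm are from 13.2 (480 × 0.8 = 384, printed as about 380). I assume one provider per survivor. The second Aim 3 hypothesis predicts improvement, so I follow the upper value.

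**Formula (normal approximation to chi-square).** Power = Φ{[d√n − 1.96√(2p̄(1−p̄))] / √(p1(1−p1) + p2(1−p2))}. For 10% versus 20%, d = 0.10 and p̄ = 0.15. The second term is 1.96 × √0.255 = 0.9897, and the denominator is √(0.09 + 0.16) = 0.5.

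**Step 1: reproduce the printed cell.** At n = 240, (1.5492 − 0.9897)/0.5 = 1.119, so power is 86.8%. Exact enumeration gives 87.4% (chi-square) and 84.6% (Fisher). The proportions detectable with 80% power at 240 per arm are 19.5% and 3.2% with the continuity-corrected formula, which round to the printed 20% and 3%. The last row of Table 10 agrees: 2.80 × √(2/240) = 0.256 SD (printed 26%), against 0.287 at 190 per arm. So the column applies neither drop-out nor provider non-response.

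**Step 2: responders needed.** n = [(0.9897 + 0.8416 × 0.5)/0.10]² = 199 per arm. Exact Fisher needs 214 and the continuity-corrected formula 219. These are 83% to 91% of 240, and all exceed 190.

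**Step 3: drop-out only.** At n = 190, (1.3784 − 0.9897)/0.5 = 0.777, so power is 78.2%. Exact values are 78.8% (chi-square) and 74.7% (Fisher).

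**Step 4: add provider non-response.** The rates below are assumptions. Powers are exact.

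| Responding providers per arm | Basis | Power, chi-square | Power, Fisher | Upper value detectable against 10% |
|---|---|---|---|---|
| 240 | nothing lost | 87% | 85% | 19-19.5% |
| 190 | 20% drop-out, full response | 79% | 75% | 20-21% |
| 152 | 80% of 190 | 69% | 64% | about 22-23% |
| 114 | 60% of 190 | 57% | 50% | about 24-25% |
| 76 | 40% of 190 | 42% | 33% | about 27-29% |
| 46 | 19% of 240 | 28% | 18% | 33.5-36% |
| 36 | 19% of 190 | 22% | 14% | 37-40% |

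As a check on the last two rows, the normal approximation gives (0.6782 − 0.9897)/0.5 = −0.623, or 26.7%, at 46 and (0.6000 − 0.9897)/0.5 = −0.779, or 21.8%, at 36.

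**The case against.** - **The 19% is not a response rate for this design.** It is the share of providers who volunteered in a study of 62 Hodgkin lymphoma survivors built around a care plan and a website. Here a survey is mailed with clinical results, up to three repeat packets follow, and an honorarium is possible if the budget permits. A reader might infer that the provider comparison will have 14% to 28% power; the documents do not support that as a prediction. The low end also needs Fisher's test together with 36 per arm, although chi-square is the named test. This objection stands, so the 19% rows serve only as a low scenario.
- **The table already covers part of the range.** The 150:150 and 75:75 columns print 22% and 28%, close to the 80% and 40% response cases. This stands too. However, the text assigns those columns to subanalyses, nothing tells the reader to use them for providers, and none goes below 75 per arm.
- **The provider count could be higher.** Participants may list more than one provider, and all designated providers are surveyed. Others may have none. The plan quantifies neither, and several providers of one survivor would not be independent observations.
- **Non-response is acknowledged.** The measures in the pitfalls paragraph address bias, and the clinical-record comparison of practice does not need a returned survey. Neither restores power for the survey outcome.
- **A reader might call this an arithmetic error in Table 10.** It is not: the cell is correct for the N it prints. The fault is that this N does not describe the provider outcome.

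**Conclusion.** The point holds as an unstated response assumption. The 240:240 detectable difference for provider self-efficacy is not delivered under the plan's own retention figure, even with full provider response. That step alone is small: 75-79% power, with the detectable value moving to about 20-21%. Non-response does the real damage. Between 80% and 40% response from 190 per arm, power for 10% versus 20% falls from about 64-69% to about 33-42%. At 19% it would be about 22-28% by chi-square (14-18% by Fisher), with roughly 33-40% detectable.

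This rests on one independent provider per survivor, on Table 9's settings applying to Table 10, and on response rates that the documents do not supply. It concerns a secondary endpoint and does not touch the Aim 2 primary analysis.

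**What to change.** In section 13.3:

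1. State under the sample size paragraph that the 240:240 column does not apply to provider outcomes.
2. Give provider outcomes their own line in Table 10, with N as responding providers per arm (survivors completing the 2nd visit × share with a designated provider × expected response) over a stated response range. Point to the 150 and 75 columns where they fit, and add a cell at about 36 to 46 per arm.
3. Report the provider comparison with confidence intervals, and state that at low response a null result is not evidence that the care plan has no effect on providers.

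The cost is some wording, one table line, and a less favourable stated detectable difference for a secondary endpoint. No participants, providers or procedures are added.

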Study Objectives	
 1. To determine the prevalence of underdiagnosis and undertreatment of common cardiometabolic conditions (i.e., hypertension, dyslipidemia, diabetes) in survivors of childhood cancer at high-risk of future serious cardiovascular disease. 2. Among survivors who are found to be underdiagnosed or undertreated, to determine (via randomized clinical trial) the efficacy of a counseling/educational intervention to improve control of these cardiometabolic conditions. 3. Determine barriers on among survivors enrolled on the randomized trial and their primary healthcare providers that contribute to undertreatment of the study's targeted cardiometabolic conditions.
Study Design	Aim 1 is an observational study. Aims 2 and 3 are based on a randomized clinical trial design.
Population	Participants in the existing Childhood Cancer Survivor Study cohort who are classified as high-risk for future cardiovascular disease based on their demographic and cancer therapy exposures.
Primary Endpoints	Aim 1: Prevalence of underdiagnosis and undertreatment of hypertension, dyslipidemia, and diabetes. Aim 2: Probability of having an undertreated condition
Secondary Endpoints	Aim 3: Determine whether intervention and control arms differ in terms of survivor knowledge, self-efficacy, and medication adherence, as well as differences in their providers' knowledge and self-efficacy related to the care of childhood cancer survivors.
Type of control	Delayed intervention control (i.e., can choose to receive the intervention at the end of the study period).
Trial Blinding	Study staff performing home visits and study statisticians will be blinded. Participants and study staff delivering the counseling intervention cannot be blinded given the nature of the study.
Treatment Groups	Group A: upfront intervention group (30 minute counseling session focused on survivorship care plan, personalized action plan; 15 minute booster session at 4 months) Group B: delayed intervention control group (30 minute counseling session focused on survivorship care plan, personalized action plan)
Treatment Schedule	Baseline: educational materials (survivorship care plan, personalized action plan, and 30 minute counseling intervention 4 months: 15 minute booster session

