Among survivors found to be underdiagnosed or undertreated (Aim 1), in a randomized controlled design, compare changes in blood pressure, lipid, and blood glucose values from baseline to 1-year between those receiving the intervention (providing clinical results and survivorship care plans [SCPs] to participants and their healthcare providers, supplemented by clinician-led remote counseling sessions with participants to review SCP contents and teach CV risk factor self-management strategies) vs. control (providing clinical results without SCP to participants and their healthcare providers; with delayed access to the intervention).

- *Hypothesis: At the 1-year follow-up home visit, survivors randomized to the intervention arm will have a lower probability of having an undertreated CV risk factor compared with survivors in the control arm.*

3.1.3 Primary Aim 3

Determine barriers among (Aim 2) survivors (at baseline and 1-year: knowledge of

past cancer treatment, self-efficacy, health-related attitudes, medication adherence) and their primary healthcare providers (at 1-year only: knowledge and self-efficacy towards childhood cancer survivorship care) that contribute to undertreatment of hypertension, dyslipidemia, and diabetes.

- *Hypothesis 1: At baseline, underdiagnosis and undertreatment will be associated with lower knowledge, self-efficacy, and medication adherence, as well as a “self-controlling” health attitude among survivors.*
- *Hypothesis 2: At 1-year follow-up, intervention-arm participants will report improved knowledge, self-efficacy, and medication adherence vs. controls; healthcare providers who received the SCP will report improved knowledge and self-efficacy towards CV risk and survivorship care vs. providers of controls.*

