7.3 Intervention Group

The intervention is a personalized clinician-led SCP-focused self-management counseling session that is generalizable to a real clinical setting. A printed SCP with personalized health history, recommendations, and clinically meaningful results from the initial home visit (i.e., average blood pressure, lipid profile, diabetes screening, BMI) will first be mailed to survivors on the intervention arm. We will then schedule participants for a remote counseling session via telephone or HIPAA-compliant web video if the participant prefers. The 1st session with a study clinician will ideally be ≤30 minutes to review the SCP and make mutually agreed upon goals and an action plan (see **Appendix**). We will ask scripted questions designed to address understanding of the SCP, elicit intentions to act on the SCP information, and elicit potential barriers and their solutions related to any planned actions. After the session, the personalized action plan will be mailed to the participant.

Approximately 4-months after the initial counseling session, participants will schedule a 2nd session by telephone, or HIPAA-compliant web video if the participant prefers, with the study clinician to follow-up on the action plan, address any barriers to the plan and mutually agree on a revised plan if needed (ideally ≤15 min). The clinician will also rate the survivor's completion of the action plan from 0 (none of the plan completed and no apparent intention to complete the plan) to 10 (action plan complete; see **Appendix**).

For the both the baseline and 4-month follow-up sessions, the duration of the sessions will be recorded to determine the feasibility of delivering the intervention within the time allotted (≤30 and ≤15 minutes, respectively). The sessions also will be audiotaped for process evaluation of content and fidelity of the clinician adherence to the intervention manual. This is further described in **Section 8**.

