7.4 Delayed Intervention Control

Survivors in the control arm will receive a copy of clinically meaningful baseline home visit results, with a general recommendation to seek medical follow-up in instances where any of those values are abnormal since we consider it unethical to withhold such information. A copy also will be sent to their designated healthcare provider. *As such, the control group's health may be improved simply by study participation.* At 4-months, participants will receive a generic thank you letter by mail for participating. This will include a reminder of the 2nd home visit, and to enhance control group retention, control participants will be told that they can receive the study intervention (minus the 4-month booster session) after completing the 2nd home visit and any associated surveys. This will include reviewing an SCP and self-management strategies with the study clinician, but we will avoid using those exact terms to minimize control group contamination.

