8.1 Baseline Questionnaire

This will include items on: 1) past medical history, 2) current health and medication adherence, 3) lifestyle habits, and 4) attitudes towards healthcare and current mood (**Table 4; Appendix**).

TABLE 4. Components of baseline questionnaire, exclusive of questions on past medical history and lifestyle habits.

*Health-related self-efficacy⁵⁶	10-item (4-point Likert scale) survey (will be reduced to 5-items) that measures perceived ability to set-goals, cope and recover from setbacks. Results have been found to be a strong predictor of subsequent health behavior change. ⁹⁶
*PROMIS anxiety & depression^{57,58}	These domains (adult 4-item survey; all 5-point Likert scale) are of secondary interest. Prior research via a longer instrument (Profile of Mood States) did not show SCPs associated with mood changes or anxiety. ^{50,85}
*Multidimensional Health Locus of Control [MHLC]⁵⁹	18-item survey (6-point Likert scale) will classify participants with regards to their attitudes towards healthcare screening into “worried”, “collaborative” and “self-controlling” typologies, which have been associated with differential likelihoods of obtaining recommended screening in retrospective CCSS analyses. ⁷⁸
*Medication Adherence Scale (MMAS-4)⁶⁰	Well-established 4-item (0=high, 1-2=medium, 3-4=low adherence) instrument initially used to study hypertension, but since validated for other diseases. ¹⁰⁰ Will be administered separately for blood pressure, lipid, and diabetes medications. Secondary analyses will examine adherence by medication burden.

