Potential pitfalls / solutions: We will closely monitor rates of abnormalities identified in Aim 1, as that influences the number of survivors eligible for Aim 2. As discussed earlier, we will oversample survivors known to have rarer target conditions (e.g., diabetes) such that the power to detect differences in Aim 2 is enhanced. Separately, given the nature of the intervention, participants and the study clinician cannot be blinded. However, exam staff will be blinded to randomization status.

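### Section 13.3 relies on randomization to make reporting bias in 1-year self-reported adherence similar across arms, but participants are unblinded and only one arm is counselled, so this does not follow

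*Combined protocol and SAP*

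**What the plan says.** Section 3.1.3 makes adherence part of a formal hypothesis: at 1 year, "intervention-arm participants will report improved knowledge, self-efficacy, and medication adherence vs. controls". Section 8.1 measures it with the MMAS-4, described as a "Well-established 4-item (0=high, 1-2=medium, 3-4=low adherence) instrument initially used to study hypertension" and given separately for blood pressure, lipid and diabetes medications. The post-intervention analysis in section 13.3 compares the arms on "survivor-reported medication adherence [t-test or Wilcoxon rank-sum"].

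Under potential pitfalls, section 13.3 concedes that self-report is less accurate than pharmacy data, explains why pharmacy data are unlikely to be feasible, and then states: "Given upfront randomization, any reporting biases should be similar across study arms". It adds that a suggestive association with adherence would support medication monitoring devices in a later study.

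On blinding, the synopsis says: "Participants and study staff delivering the counseling intervention cannot be blinded given the nature of the study". Section 13.2 repeats that "given the nature of the intervention, participants and the study clinician cannot be blinded". Exam staff and statisticians are blinded.

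**The concern.** The sentence gives randomization as the reason why reporting bias should be alike in the two arms. That reason covers only what exists before allocation. The adherence outcome is a questionnaire answered about a year later by people who know their arm and have had very different contact with the study. How they answer can itself depend on arm.

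At stake is the reading of one Aim 3 result. If the MMAS-4 differs between arms, the plan as written lets the difference be read as a change in medication taking, because reporting has been set aside as balanced. The design does not support that step, and the plan has no analysis showing how much differential reporting it would take to explain the finding.

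**Working it through.** **Step 1. What each arm has experienced before the 1-year questionnaire.**

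| | Intervention | Control |
|---|---|---|
| After 1st home visit (7.3, 7.4, 8.4) | Results, survivorship care plan, counselling session, agreed action plan | Results, with general advice to seek follow-up of abnormal values |
| Content of contact (7.3) | Scripted questions that "elicit potential barriers and their solutions related to any planned actions" | None |
| 4 months (7.3, 8.6) | Second session; clinician rates plan completion from 0 to 10 | Generic thank-you letter |
| Access to counselling | Before the outcome | After it: "control participants will be told that they can receive the study intervention (minus the 4-month booster session) after completing the 2nd home visit" |
| Knows own arm (synopsis, 7.2, 13.2) | Yes | Yes |

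The rows differ only because of what happens after allocation, so randomization cannot balance their effect on answers. Blinding exam staff and statisticians does not change what a participant enters in a questionnaire.

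**Step 2. Comparison with providers.** Later in the same paragraph of 13.3, the plan recognizes that intervention-arm providers might be more motivated to respond. It plans response monitoring, a comparison of responders with non-responders, and a sensitivity analysis. Survivor-reported adherence gets no such analysis.

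**Step 3. Reproduce the plan's own figure.** Table 10 gives detectable differences for the MMAS-4 as a percentage of 1 SD. Assume two-sided α = 0.05 and 80% power, which the text does not state for Table 10. Then

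MDD = (1.960 + 0.842) × √(1/n₁ + 1/n₂)

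| n₁ : n₂ | Computed | Table 10 |
|---|---|---|
| 320:480 | 0.202 SD | 20% |
| 240:240 | 0.256 SD | 26% |
| 150:150 | 0.324 SD | 33% |
| 75:75 | 0.458 SD (0.461 with t) | 46% |

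The arithmetic of that row is sound. The point concerns interpretation, not power.

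**Step 4. Effect of a one-arm reporting shift.** Let the true effect be zero and let the mean score in one arm shift by b SD through reporting alone. For a two-sided 5% comparison of means,

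SE = √(2/n), P(reject) = Φ(b/SE − 1.96) + Φ(−b/SE − 1.96).

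Inputs not in the documents:
- b is assumed, from 0.05 to 0.20 SD.
- The number of medication users per arm is not stated. I take 40 per arm as an assumption. I also use 75, the smallest group size in Table 10, although there it refers to a subanalysis by diagnosis status and not to medication users.

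Worked case, n = 40 and b = 0.20: SE = √(2/40) = 0.2236; b/SE = 0.894; Φ(−1.066) + Φ(−2.854) = 0.143 + 0.002 = 0.145.

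| Shift b | 40 per arm (SE 0.2236) | 75 per arm (SE 0.1633) |
|---|---|---|
| 0 | 5.0% | 5.0% |
| 0.05 SD | 5.6% | 6.1% |
| 0.10 SD | 7.3% | 9.4% |
| 0.15 SD | 10.3% | 15.1% |
| 0.20 SD | 14.5% | 23.2% |

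The formula is symmetric in b, so these rates do not depend on which arm shifts or in which direction.

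**The case against.** The best defence has several parts.

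- **The wording is hedged.** The plan says biases should be similar, not that they are equal. That is so, but the reason it gives still does not apply to a post-randomization, unblinded self-report.
- **The plan is already cautious.** It admits the weakness of self-report, calls a finding suggestive and points to objective monitoring later. Sections 8.8, 13.2 and 13.3 also compare measured values, prescriptions and treatment intensity by arm. This stands and lowers the stakes. None of it is linked to the adherence result, however, and the suggestive association could equally be the baseline one, where bias by arm cannot arise.
- **The demand effect may be small or run the other way.** The follow-up questionnaire is normally mailed to both arms, months after the 4-month session, and is not described as collected by the counselling clinician (8.7). Sessions that explore barriers might make people more candid. This also stands: direction and size are unknown.

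A reader might infer that the bias must favour the intervention, or that false positives would be frequent because 190 or 240 per arm would be analysed. The documents support neither. Those counts cover all completers or all randomized participants, while the MMAS-4 applies only to users of each drug class. A reader might also want measured values to decide whether an adherence claim is allowed. That would be unsound: measured values also move through lifestyle change and treatment intensification, and records show prescribing, not intake.

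**Conclusion.** The point holds as a correction to one inference and to how one secondary result is read. Randomization does not secure similar reporting across arms at 1 year, and a difference in MMAS-4 could be partly or wholly a reporting difference. It need not be; nothing in the documents shows that such bias will occur.

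Under the assumed shifts of 0.05 to 0.20 SD and no true effect, the chance of a significant difference rises from 5% to about 6 to 15% at 40 users per arm, and to about 6 to 23% at 75 per arm. These figures rest on the assumed shift, the assumed number of users, a normal approximation to the planned t-test, and a shift confined to one arm.

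It would be wrong to carry this over to Aim 2. Its primary endpoint rests on measured blood pressure and blood values and is not affected by this sentence.

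**What to change.** 1. Replace the sentence in 13.3. State that randomization balances baseline reporting tendencies only, and that 1-year survivor-reported adherence is an unblinded self-report open to differential reporting.
2. Prespecify a simple sensitivity analysis: for each medication class, report the one-arm reporting shift, in MMAS-4 points and in SD, that would reduce the observed difference to zero. Give the number of medication users per arm beside it. State the scoring direction first, because section 8.1 scores 0 as high adherence while the baseline analysis in 13.3 equates lower adherence with lower mean scores.
3. Show each class-specific adherence difference next to the planned arm comparisons of the matching measured values and abstracted medication records. Label these as supporting context, not as a pass/fail condition for an adherence claim.

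The cost is a change of wording and one extra table. No new data, visits or participants are needed. The downside is a more cautious conclusion on adherence.
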